### **8.3.5. Pregnancy Testing**

Refer to [Section 5.1](#) inclusion criteria for pregnancy testing entry criteria.

Pregnancy testing (serum or urine) should be conducted for women of CBP as detailed in the SoA ([Section 1.3](#)).

Additional serum or urine pregnancy tests may be performed, as determined necessary by the investigator or required by local regulation, to establish the absence of pregnancy at any time during the participant's participation in the study.

### **8.3.6. Suicidal Ideation and Behavior Risk Monitoring**

ASMs are associated with an increased risk of suicidal ideation or behavior.

Participants with EMAS may occasionally develop suicidal ideation or behavior.

Participants being treated with IMP should be monitored appropriately and observed closely for suicidal ideation and behavior or any other unusual changes in behavior, especially at the beginning and end of the course of IMP, or at the time of dose changes, either increases or decreases. All factors contributing to suicidal ideation or behavior should be evaluated and consideration should be given to discontinuation of the IMP.

Baseline assessment of suicidal ideation and behavior will be monitored during the study using C-SSRS or clinical interview if C-SSRS is not appropriate.

## **8.4. Adverse Events, Serious Adverse Events and Other Safety Reporting**

The definitions of AEs and SAEs can be found in [Section 10.4](#) (Appendix 4).

AEs will be reported by the participant (or, when appropriate, by a caregiver, surrogate, or the participant's legally authorized representative).

The investigator and any qualified designees are responsible for detecting, documenting, and recording events that meet the definition of an AE or SAE and remain responsible for following up all AEs or SAEs, considered related to the IMP or study procedures, or that caused the participant to discontinue the IMP until resolution or the event is considered stable (see [Section 7](#)).

The method of recording, evaluating, and assessing causality of AEs and SAEs and the procedures for completing and transmitting SAE reports are provided in [Section 10.4](#) (Appendix 4).

#### **8.4.1. Time Period and Frequency for Collecting AE and SAE Information**

All AEs\*, including SAEs, will be collected from the signing of the ICF until the follow-up visit (Visit 11 for Part A and Visit 12 for Part B) as specified in the SoA ([Section 1.3](#)) or end of the participant's participation in the study.

Medical occurrences that begin before the start of IMP but after obtaining informed consent/assent will be reported as non-TEAE.

All SAEs will be recorded and reported to the sponsor or designee immediately and under no circumstance should this exceed 24 hours of becoming aware of the SAE as indicated in [Section 10.4](#) (Appendix 4). The investigator will submit any updated SAE data to the sponsor within 24 hours of it being available.

Investigators are not obligated to actively seek information on AEs or SAEs after conclusion of the study participation. However, if the investigator learns of any SAE, including a death, at any time after a participant has been discharged from the study, and he/she considers the event to be reasonably related to the IMP or study participation, the investigator must promptly notify the sponsor.

\* For the participant's expected seizure types, these do not routinely require documentation as AEs. However, any clinically significant worsening, including a clinically significant change in the pattern or severity of seizures from baseline, must be documented as an AE.

#### **8.4.2. Method of Detecting AEs and SAEs**

Care will be taken not to introduce bias when detecting AEs and/or SAEs. Open-ended and non-leading verbal questioning of the participant is the preferred method to inquire about AE occurrences.

#### **8.4.3. Follow up of AEs and SAEs**

After the initial AE/SAE report, the investigator is required to proactively follow each participant at subsequent visits/contacts. All SAEs, and AEs of special interest (as defined in [Section 10.4.3](#)), will be followed until resolution, stabilization, the event is otherwise explained, or the participant is lost to follow-up (as defined in [Section 7.3](#)). Further information on follow-up procedures is provided in [Section 10.4.4](#).

#### **8.4.4. Regulatory Reporting Requirements for SAEs**

Prompt notification by the investigator to the sponsor of an SAE is essential so that legal obligations and ethical responsibilities towards the safety of participants and the safety of an IMP under clinical investigation are met.

The sponsor has a legal responsibility to notify both the local regulatory authority and other regulatory agencies about the safety of an IMP under clinical investigation. The sponsor will comply with country-specific regulatory requirements relating to safety reporting to the regulatory authority, IRB/IEC, and investigators.

An investigator who receives an investigator safety report describing an SAE or other specific safety information (eg, summary or listing of SAEs) from the sponsor will review and then file it

along with the IB/package insert and will notify the IRB/IEC, if appropriate according to local requirements.

Investigator safety reports must be prepared for suspected unexpected serious adverse reactions according to local regulatory requirements and sponsor policy and forwarded to investigators as necessary.

#### **8.4.5. Pregnancy**

Details of all pregnancies in female participants and, if indicated, female partners of male participants will be collected after the ICF has been signed and until 3 months after the follow-up visit (Part B Visit 11 or Part A Visit 12 [if the participant does not continue to Part B]).

If a pregnancy is reported, the investigator will record pregnancy information on the appropriate form and submit it to the sponsor within 24 hours of learning of the female participant or female partner of male participant pregnancy.

The investigator is not obliged to actively monitor for any pregnancies that commence more than 3 months after the follow-up visit. However, if the investigator becomes aware of a new pregnancy outside this time limit, then they should report it as above. The sponsor PVD will follow-up for all pregnancy outcomes.

While pregnancy itself is not considered to be an AE or SAE, any pregnancy complication or elective termination of a pregnancy for medical reasons will be reported as an AE or SAE.

Abnormal pregnancy outcomes (eg, spontaneous abortion, fetal death, stillbirth, congenital anomalies, ectopic pregnancy) are considered SAEs and will be reported as such.

The participant/pregnant female partner (after obtaining the necessary signed informed consent/assent from the female partner) will be followed to determine the outcome of the pregnancy. The investigator will collect follow-up information on the participant/pregnant female partner and the neonate for 6 months after birth, and the information will be forwarded to the sponsor.

Any post-study pregnancy-related SAE considered reasonably related to the IMP by the investigator will be reported to the sponsor as described in [Section 8.4.4](#). While the investigator is not obligated to actively seek this information in former study participants/pregnant female partner, he or she may learn of an SAE through spontaneous reporting.

Any female participant who becomes pregnant while participating in the study will discontinue IMP or be withdrawn from the study.

#### **8.4.6. Adverse Events of Special Interest**

See [Section 10.4.3](#).

### **8.5. Pharmacokinetic Assessments**

PK assessments will only be performed for Part A of the study. Plasma samples will be collected from all participants for measurement of plasma concentrations of CBD and its major metabolites as specified in the SoA ([Section 1.3](#)) as follows:

- Pre-dose (within 60 minutes prior to the morning dose of IMP).

- Post-dose (3 hours [ $\pm 1$  hour]) following morning dose of IMP).

Instructions for the collection and handling of biological samples will be provided by the sponsor. The actual date and time (24-hour clock time) of each sample will be recorded.

Samples will be used to evaluate the PK of CBD and its major metabolites.

IMP concentration information that may unblind the study will not be reported to investigative sites or blinded personnel until the study has been unblinded.

The maximum amount of blood taken for PK analysis will be approximately 4 mL.

Caregivers will record the date, time, and meal type (eg, high fat meal [dairy or meat], standard meal [fruit or vegetable] or other [if not fitting into one of the categories above]) for all meals consumed by the participant within 24 hours prior to PK collection.

Analysis of all PK samples will be conducted at a central bioanalytical laboratory and additional details are provided in the laboratory manual.

## **8.6. Pharmacodynamic Assessment**

Pharmacodynamic parameters are not evaluated in this study.

## **8.7. Genetics Assessment**

In Part A, samples for epilepsy gene panel analysis will be collected at the time point indicated in the SoA ([Section 1.3](#)), if the participant/caregiver/legal representative provides consent/assent.

Participation is optional. Participants who do not wish to participate in the genetic research may still participate in the study.

Details on processes for collection, shipment, storage, and destruction of these samples can be found in a separate laboratory manual. No genetic samples will be retained following the analysis.

## **8.8. Biomarkers**

Biomarkers are not evaluated in this study.

## **8.9. Immunogenicity Assessments**

Immunogenicity assessments are not evaluated in this study.

## **8.10. Healthcare Resource Utilization**

Healthcare resource utilization parameters are not evaluated in this study.

## **8.11. Special Circumstances**

During special circumstances (eg, COVID-19 pandemic), the specific guidance from local public health and other competent authorities regarding the protection of individuals' welfare must be applied. In cases where participants are not able to perform all protocol-defined assessments due to special circumstances, the investigator must discuss with the medical monitor potential mitigation approaches.

For the duration of such special circumstances, the following measures may be implemented for enrolled participants:

- Visits may be done by a telephone call, other means of virtual contact or home visit, if appropriate.
- Participant and/or clinician-rated outcomes assessments may be done by videoconference, telephone call, other means of virtual contact, if possible.
- An alternative approach for IMP dispensing, secure delivery, and collection may be sought.
- Visits may take place in a different location than defined in the protocol. If this is not feasible, then the visit may take place virtually with documentation of the means of communication (eg, phone call or videoconference).
- Biological samples may be collected and analyzed at a different location than defined in the protocol. Biological samples should not be collected if they cannot be processed in a timely manner or appropriately stored until shipping/processing.
- If it is not possible to collect the biological samples or safety assessments (eg, ECG, vital signs) within the interval predefined in the protocol (see the SoA [[Section 1.3](#)]), then the interval may be extended up to a maximum duration of 7 days.
- If a safety assessment cannot be performed within the modified window, the investigator must review the benefit-risk for participant continuation in the study and record this in the medical records.

The rationale (eg, the specific reasons behind the changes) and outcome of the discussion with the medical monitor will be documented in the medical record. Information on how each visit was performed will be recorded in the eCRF.

## 9. STATISTICAL CONSIDERATIONS

### 9.3. Analysis Sets

For the purposes of analysis, the following analysis sets are defined:

Participant Analysis Set	Description
Enrolled	All participants who sign the ICF.
Randomized	All Enrolled participants who are randomized to IMP. This analysis set will be used to summarize randomized participants in the participant disposition summary table.
Part A ITT	
All participants in Part A who are randomized, receive at least 1 dose of IMP during Part A, and have post-baseline efficacy data.
 
Participants will be analyzed according to their randomized treatment group. The Part A ITT analysis set is the primary analysis set for all efficacy endpoints in Part A.

Part A Safety	
All randomized participants who are exposed to IMP.
 
Participants will be analyzed according to the IMP they receive.

Part B Safety	All participants who enter Part B and receive at least 1 dose of IMP during Part B will be included.

Abbreviations: ICF = informed consent form; IMP = investigational medicinal product; ITT = intention to treat.

## 9.4. Statistical Analyses

The interim analysis SAP, SAP and ADR will be finalized prior to the first interim analysis and will include a more technical and detailed description of the statistical analyses described in this section. This section is a summary of the planned methodology.

#### 9.4.1. General Considerations

Unless stated otherwise, continuous data will be summarized using descriptive statistics comprising the number of participants with data to be summarized (n), mean, SD, median,

minimum (min), and maximum (max). Categorical variables will be summarized by the frequency and proportion of participants falling into each category.

For plasma concentration data and PK parameters, geometric mean, CV, and geometric CV will also be computed.

Unless stated otherwise, baseline is defined as the last record or measurement collected prior to the first dose of IMP on Day 1 (Part A Visit 3). Baseline for Part B is the same as the baseline for Part A.

#### **9.4.2. Primary Endpoint(s)**

##### **Part A:**

The primary efficacy endpoint is EMAS-associated seizure frequency (myoclonic-atomic, atomic, tonic, clonic, or tonic clonic) over the 14-week treatment period.

The primary estimand for this study is defined by the following 3 components:

- Target population: participants with EMAS-associated seizures who have not achieved adequate control from other ASMs.
- Endpoint: change in EMAS-associated seizure frequency during the 14-week treatment period compared to baseline.
- Measure of IMP effect: change in EMAS-associated seizure frequency during the treatment period, regardless of any intercurrent events. This measure of effect follows the treatment policy strategy for handling intercurrent events.

The analysis of the primary efficacy endpoint will utilize Bayesian methodology to borrow external data from the historical pivotal studies in DS, LGS, and TSC. Active treatment groups will be pooled across doses within each indication to achieve a single estimated historical treatment effect for each indication. A Bayesian hierarchical model that dynamically determines the amount of information to be “borrowed” from the historical studies in the estimation of the treatment effect in the EMAS population will be used ([Viele 2014](#)).

For the primary efficacy analysis, a single Bayesian hierarchical linear model will be applied as specified in the interim analysis SAP, SAP, and ADR to the 4 populations (DS, LGS, TSC, and EMAS). The model will include a population-specific intercept, a population-specific treatment effect, an adjustment for prespecified baseline covariates (log baseline seizure frequency, age at onset of seizures, and clobazam use), and a shared residual error. Prior distributions are prespecified for each of the model parameters. A Bayesian hierarchical distribution is specified for the treatment effects across populations, in which each study-specific treatment effect has a normal distribution centered on a grand overall treatment effect. A prior on the variance of this distribution will be specified to induce dynamic borrowing of the data from the previous pivotal trials in DS, LGS and TSC, in which the degree of similarity of the EMAS observed data relative to the historical data influences the magnitude of borrowing. Markov-Chain Monte Carlo methods will be used to estimate the Bayesian posterior distribution for parameters in the primary analysis model. Statistical inference and hypothesis testing will be conducted on the EMAS-specific treatment effect parameter corresponding to the primary efficacy hypothesis (ie, ratio of the change in seizure frequency between GWP42003-P and placebo). Complete details will be provided in the interim analysis SAP, SAP, and ADR.

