#### 2.1.2. Study Intervention Background

GWP42003-P is the product code for the IMP, purified GWP42003-P, a CBD under development by the sponsor for the treatment of a number of conditions.

CBD is extracted from the *Cannabis sativa* L. plant as CBD BDS and purified by crystallization from solvent to produce the CBD active substance.

Nonclinical pharmacology studies conducted by the sponsor have identified antiepileptic, anti-inflammatory, neuroprotective, and antipsychotic activities for CBD.

A large body of nonclinical toxicity data on purified CBD and CBD BDS suggests a good safety profile for CBD and a wide safety margin between the proposed clinical dose of CBD and the dose at which toxicity is noted.

There is an adequate margin of safety for CBD at a daily dose of up to 25 mg/kg/day in a pediatric and adult population.

A single ascending-dose study has been conducted where 4 groups of 6 healthy participants received single oral doses of either 1500, 3000, 4500, or 6000 mg GWP42003-P (GWEP1544). Each single oral dose was well or moderately well tolerated.

The sponsor has performed a number of clinical studies to investigate a range of possible indications for GWP42003-P. These include 5 positive pivotal studies that have supported its commercialization in the US, EU, and other geographic expansion areas as an ASM.

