## 2.2. Study Rationale

There are no FDA-approved treatment options specifically for EMAS and its associated primary seizure types (ie, myoclonic-ataxic and/or atonic and/or myoclonic seizures) and no clear consensus treatment guidelines for EMAS. Drug resistance to ASMs in children with EMAS is common and patients typically fail an average of 5 ASMs (Doose 1970) (Oguni 1992). While several ASMs, including valproic acid, clobazam, clonazepam, and levetiracetam have been reported to be beneficial, none of these agents have been evaluated in randomized, controlled studies in patients with EMAS. Furthermore, most of these ASMs have also been associated with safety and tolerability issues, such as sedation, ataxia, and cognitive impairment (Menlove 2015). Valproic acid may have the best efficacy for controlling myoclonic seizures, but it is associated with additional safety and tolerability issues (eg, risk for hepatotoxicity, teratogenicity, alopecia, etc.). EMAS is considered challenging to treat and often requires patients to tolerate difficult-to-maintain ketogenic diets (Goldberg 2001). Despite all the treatment options with ASMs and ketogenic diet, 20 to 50% of patients will not respond to treatment and only 50% will become seizure free (Kelley 2010) (Helmstaedter 2020). Thus, there is a clear unmet need for the development of effective and well-tolerated treatments that target the primary seizures associated with EMAS.

Based on the results of several Phase 3 studies and open-label studies with GWP42003-P in the treatment of other pediatric epilepsy syndromes, GWP42003-P may be an appropriate candidate to investigate for the treatment of EMAS. Results of 5 Phase 3 randomized, double-blind, placebo-controlled studies show robust efficacy of GWP42003-P for treatment of seizures associated with LGS (Devinsky 2018a) (Thiele 2018), DS (Devinsky 2017) (Miller 2020), and TSC (Thiele 2020b). These effects were sustained with long-term therapy up to 1.5 years (Devinsky 2016). There is also strong preclinical (Gofshteyn 2017) (Hess 2016) and real-world evidence (Devinsky 2016) (Devinsky 2018b) (Szaflarski 2018) (Thiele 2020a) suggesting that GWP42003-P might have antiepileptic properties that target a broad range of seizure types.

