## 4.2. Scientific Rationale for Study Design

EMAS is characterized by multiple seizure types (myoclonic-atomic, myoclonic, atomic, generalized tonic-clonic, atypical absences, and tonic seizures), with myoclonic-atomic seizures being the hallmark seizure type and mandatory for the diagnosis of EMAS ([Hinokuma 2020](#)) ([Kelley 2010](#)) ([Neubauer 2005](#)). There are no FDA-approved treatment options specifically for EMAS and its associated primary seizure types (ie, atomic and/or myoclonic seizures), and no clear consensus treatment guidelines for EMAS. Drug resistance to ASMs in children with EMAS is common and patients are typically exposed to and fail an average of 5 ASMs ([Doose 1970](#)) ([Oguri 1992](#)). While several ASMs have been reported to be beneficial, none of these agents have been evaluated in randomized, controlled studies in EMAS patient. Furthermore, most of these ASMs have also been associated with safety and tolerability issues, such as sedation, ataxia, and cognitive impairment ([Menlove 2015](#)). EMAS is considered challenging to treat, often requiring patients to tolerate difficult-to-maintain ketogenic diets ([Goldberg 2001](#)). Despite all the treatment options with ASMs and ketogenic diet, 20 to 50% of patients do not respond to treatment and only 50% become seizure-free ([Helmstaedter 2020](#)) ([Kelley 2010](#)). Thus, there is a clear unmet need for the development of effective and well-tolerated treatments that target the primary seizures associated with EMAS.

Based on the results of several Phase 3 studies and open-label studies with GWP42003-P in the treatment of other pediatric epilepsy syndromes, GWP42003-P may be an appropriate candidate to investigate for the treatment of EMAS. Results of 5 Phase 3 randomized, double-blind, placebo controlled studies show robust efficacy of GWP42003-P for treatment of seizures associated with LGS ([Devinsky 2018a](#)) ([Thiele 2018](#)), DS ([Devinsky 2017](#)) ([Miller 2020](#)), and TSC ([Thiele 2020b](#)). The anticonvulsant efficacy of GWP42003-P was durable as effects were sustained up to 1.5 years ([Devinsky 2016](#)).

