GWP42003-P was also investigated in patients with other treatment-resistant epilepsies in the investigator initiated, FDA authorized EAP (including those with EMAS). Interim safety and efficacy results from the EAP uphold the finding that GWP42003-P produces clinically significant reductions in seizures when used as an add-on ASM treatment ([McCagh 2009](#)) ([Wu 2020](#)). Thus, there is direct evidence supporting that GWP42003-P can be an effective therapy for treatment of EMAS associated seizures.

Given the extensive clinical study results that have established the safety and efficacy profile of GWP42003-P as an anticonvulsant therapy and its potential to address the existing unmet need in the EMAS, the primary aim of Part A of the study is to assess the efficacy of GWP42003-P compared to placebo as an adjunctive treatment for children with EMAS. The primary aim of Part B of the study is to evaluate the long-term safety and tolerability of GWP42003-P in participants with EMAS.

The choice of a flexible dosing approach was based on results of the Phase 3 studies for DS, LGS, and TSC with GWP42003-P. These studies suggest that participants randomized to lower maximum dosages of GWP42003-P (eg, 10 mg/kg/day) experienced a similar magnitude of reductions in seizures to those treated with higher dosages of GWP42003-P (eg, 20, 25, and 50 mg/kg/day). Likewise, participants randomized to higher doses of GWP42003-P in clinical

studies report significantly greater side effects compared to those randomized to lower doses. However, given the variability in dose-response to GWP42003-P, it is possible that AEs observed with higher doses of GWP42003-P could be mitigated if participants are only titrated when clinically indicated. The choice of treatment length was determined based on previous studies of GWP42003-P, which have demonstrated that onset of treatment effect occurs rapidly (approximately within the 1 to 2 weeks of treatment) and maximum efficacy is attained at around 1 month of treatment. Based on these results, it is not scientifically warranted to extend the treatment phase past the length of historic studies (14 weeks).

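### The borrowing model lists one intercept per indication, so the DS and LGS effects lent to EMAS can absorb between-trial differences unless the ADR adds a trial term

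*Combined protocol and SAP*

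**What the plan says.** Section 9.4.2 (Part A) fits a single Bayesian hierarchical linear model to four populations: DS, LGS, TSC and EMAS. Its terms are given as: "The model will include a population-specific intercept, a population-specific treatment effect, an adjustment for prespecified baseline covariates". The covariates are log baseline seizure frequency, age at seizure onset and clobazam use, and the residual error is shared. No trial-level intercept or stratum is named.

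The same section states how the historical data are combined: "Active treatment groups will be pooled across doses within each indication to achieve a single estimated historical treatment effect for each indication". It then describes the hierarchical distribution for the treatment effects as one "in which each study-specific treatment effect has a normal distribution centered on a grand overall treatment effect", which names the study, not the population, as the unit.

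The historical data come from more trials than there are populations. Section 2.2 says: "Results of 5 Phase 3 randomized, double-blind, placebo-controlled studies show robust efficacy of GWP42003-P for treatment of seizures associated with LGS". The sentence goes on to DS and TSC and cites two reports for LGS, two for DS and one for TSC. Section 4.2 repeats this, and Section 2.1.2 also counts five: "These include 5 positive pivotal studies that have supported its commercialization".

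Section 9.4 calls this text a summary. Section 9.4.2 defers complete details to the interim analysis SAP, the SAP and the ADR. Under Section 9.4 these are to be finalized before the first interim analysis.

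**The concern.** Randomization protects the comparison of active with placebo inside each trial. With one intercept for DS and one for LGS, participants on active drug in one trial are also compared with placebo participants in the other. If the two trials have different background levels after covariate adjustment, and one contributes relatively more of the active participants than of the placebo participants, part of the background difference is counted as drug effect.

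Unequal splits are plausible, though not shown. Active arms are pooled across doses, Section 4.2 names several historical dose levels (10, 20, 25 and 50 mg/kg/day), and in the reference list one of the two DS reports is titled as a dose-ranging trial while the other is not.

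Inference on the primary hypothesis uses the EMAS-specific effect, which is shrunk toward the historical effects. An error in DS or LGS therefore reaches the primary test. By Section 9.4.3.1, the responder and CGIC models take a similar form and total seizure frequency is analyzed as the primary endpoint is, so the issue repeats there.

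**Working it through.** The plan gives no figure to reproduce: the sample size reasoning and the borrowing prior are not in the available text. The check is therefore on structure and then on size. All numerical inputs below are assumptions unless a section is named. Effects are log ratios.

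**1. Structure.** Five historical trials (Sections 2.1.2, 2.2, 4.2) share three historical intercepts (Section 9.4.2). TSC has one trial, so its population intercept is already a trial intercept. Only DS and LGS are exposed.

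**2. Bias in one indication.** Let d be the difference in intercept between the two trials after covariates. With one intercept in a linear model,

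bias = d × (trial 2's share of active participants − trial 2's share of placebo participants).

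Assume trial 1 has 60 active and 60 placebo, and trial 2 has 120 active and 60 placebo:

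120/180 − 60/120 = 0.667 − 0.500 = 0.167.

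| Shift d | Bias = 0.167 × d |
|---|---|
| 0.2 | 0.033 |
| 0.3 | 0.050 |
| 0.5 | 0.083 |

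The sign follows d and which trial has the higher split, so the error can favor either arm.

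A noiseless least-squares fit agrees. With a true log ratio of −0.300 and d = 0.2, one intercept returns −0.267 and trial intercepts return −0.300. With 1:1 in both trials, one intercept also returns −0.300. A simulation with noise (residual SD 0.9, 4,000 replicates) gave biases of −0.051 at d = −0.3 and −0.083 at d = −0.5 with one intercept, and 0.004 or less with trial intercepts.

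For other trial sizes (size ratio 1 to 2), the multiplier is 0.156 to 0.171 for splits of 1:1 and 2:1, and 0.250 to 0.267 for 1:1 and 3:1. It is exactly zero for equal splits.

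**3. Carry-over to EMAS.** This uses a normal-approximation hierarchical model with a half-normal prior (scale 0.1 to 0.5) on the between-population SD, integrated on a grid. Other inputs:
- residual SD 0.9
- DS and LGS each sized as in step 2
- TSC 150 active and 75 placebo
- EMAS 30 to 60 per arm (60 per arm is the maximum in Section 4.4)
- true historical log ratio −0.3, with an EMAS estimate of −0.3 or 0

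Shift in the EMAS posterior mean:

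| Bias per affected indication | DS and LGS same direction | Only one biased | Opposite directions |
|---|---|---|---|
| 0.02 | 0.005 to 0.012 | 0.003 to 0.006 | 0 to 0.001 |
| 0.05 | 0.014 to 0.031 | 0.008 to 0.015 | 0 to 0.005 |
| 0.083 | 0.026 to 0.051 | 0.015 to 0.026 | 0 to 0.014 |

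A bias of 0.02 corresponds to a shift of 0.02/0.167 = 0.12. With opposite directions the result is zero when the EMAS estimate agrees with history; the upper values arise when the EMAS estimate is null.

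A cruder check uses equal weights on the three historical effects and fixed shrinkage B: EMAS shift = B × 2/3 × bias. For B from 0.2 to 0.8 and biases from 0.0167 to 0.05, this gives 0.002 to 0.027, the same order of magnitude.

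**4. Scale.** The EMAS-only standard error is 0.9 × √(2/60) = 0.16 at 60 per arm and 0.9 × √(2/30) = 0.23 at 30 per arm. The largest shifts are 0.051 at 30 per arm and 0.045 at 60 per arm, or 0.051/0.232 = 0.22 and 0.045/0.164 = 0.27 of that standard error.

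**5. Price of trial intercepts.** One intercept: SE = 0.9 × √(1/180 + 1/120) = 0.106. Trial intercepts: the information is 60×60/120 + 120×60/180 = 30 + 40 = 70, so SE = 0.9/√70 = 0.108. The increase is √(72/70) − 1 = 1.4%, where 72 = 180×120/300.

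**The case against.** The strongest reply is that the text is an openly labelled summary. The interim analysis SAP, the SAP and the ADR carry the full model and may already contain a trial term. This stands, and it is why the point is conditional. It does not dispose of the point: the protocol lists specific model terms, and a trial term is not among them.

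A reader might infer that the historical effect lent to EMAS is not a randomized comparison, or that it is biased. The documents do not support either reading. Bias needs both unequal splits and unequal adjusted intercepts within an indication, and neither is documented. Section 4.2 names dose levels, not arms or allocations per trial. Most of each DS and LGS contrast remains within-trial, and TSC is wholly so.

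The top of the range also stacks assumptions. A shift of 0.5 means a background level 65% higher (e^0.5 = 1.65) in one of two trials in the same indication after covariate adjustment. Nothing in the documents supports a shift that large, nor the same sign in DS and LGS.

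Section 9.4.2.2 plans fixed-borrowing analyses from full to no borrowing. The no-borrowing end is free of this bias and would show whether the conclusion depends on borrowing. It does not correct the historical effects, and the full-borrowing end carries the error forward.

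Finally, it is tempting to read the study-specific wording as a second model with five historical effects. Section 9.4.2 itself fixes the unit as one effect per indication, so this is a wording slip.

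**Conclusion.** The point holds in conditional form. As summarized, the model does not keep the DS and LGS comparisons within trial by construction. Under the assumed 1:1 and 2:1 splits and shifts of about 0.12 to 0.5, the EMAS posterior mean would move by about 0.005 to 0.05 log units if both indications are biased alike, about half that if one is, and little or nothing if the biases oppose. That is at most roughly a quarter of the EMAS-only standard error, in an unknown direction. With matching splits there is no bias at all.

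The expected gain is modest, but the error is avoidable at almost no statistical cost and affects the quantity on which the primary hypothesis is tested. The change is worth making before the analysis documents are finalized. The actual splits and between-trial differences, which the sponsor holds, would settle the size.

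**What to change.** In Section 9.4.2 and the ADR:
- Replace the population-specific intercept with a trial-specific intercept (five historical trials plus EMAS), and keep one treatment effect per indication.
- Make the same change in the key secondary models of Section 9.4.3.1.
- In the description of the hierarchical distribution, change study-specific to population-specific so that one unit is named throughout.

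If the ADR already has trial intercepts, only the protocol summary needs correcting.

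The cost is two extra nuisance parameters (six intercepts in place of four) and a standard error about 1 to 2% wider for the DS and LGS effects. No new data are needed. Because the statistical methods were revised after consultation with the FDA under its Complex Innovative Trial Design program, the change may also call for a re-run of the design simulations, and presumably agreement with the agency, before the ADR is finalized.
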